3.1 Study Design

This survey will be completed by a sample of healthcare providers who were targeted to receive the metabolic educational materials and either currently prescribe or have the potential to prescribe SEROQUEL or SEROQUEL XR. A sample of healthcare providers who were targeted for the educational materials will be approached to participate in the survey.

The survey will be administered using the following modality:

• Self-administered and Internet-based questionnaire accessed through a secure website instructing the participant to enter a unique code provided in the invitation.

The survey will begin with screening questions to confirm respondent eligibility to participate in the survey. Completion of the entire survey is expected to take less than 10 minutes.

The survey included in Appendix B is written to reflect the wording and screen-by-screen presentation of questions for an Internet-based survey administration.

All respondents who complete the survey and who provide their contact information will be mailed a fee consistent with approved market value for the physician's time for completing the survey.

The questions related to having received the educational materials and having read the information (measures of process) are closed-ended questions (answered affirmatively as yes/no/unsure response options). Questions related to physician behavior regarding monitoring of patients (measures of outcome) are percentage estimates provided by the physician.

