3.1.1 Questions Regarding Key Monitoring Behavior

Question 1:

What is your medical specialty*? Please select one from the drop-down list below.

- O General Medicine/General Practice
- O Neurology
- O Psychiatry
- O Other SPECIFY:

* NOTE – OTHER SPECIALTIES TO BE INCLUDED BASED ON AUDIENCES TO WHOM MATERIAL WAS SENT

Question 2

Please think about your patients with schizophrenia, bipolar disorder, and/or major depressive disorder who are treated with Seroquel® or Seroquel® XR. Describe the "monitoring" of metabolic factors^{*} potentially related to treatment with Seroquel® or Seroquel® XR.

A. What proportions of your patients are being monitored by you, someone else in your practice or are referred to other healthcare providers? _____%

B. What proportion of your patients is referred to other healthcare providers for monitoring?

*Monitoring of metabolic factors includes: weight at initiation and during continuing treatment, ordering or reviewing lipid panel tests, observing patients for signs or symptoms associated with hyperglycaemia, ordering or reviewing tests for blood glucose measurement for patients with diabetes mellitus or in patients with risk factors for diabetes mellitus for worsening of glycaemic control, and counseling on nutrition, exercise and maintaining a healthy lifestyle

Question 3

Thinking now of the patients that you (or someone in your practice) monitor for metabolic issues potentially related to treatment with Seroquel® or Seroquel® XR, which of the following activities do you do? Please check all that apply.

- [□] I counsel patients taking Seroquel® or Seroquel® XR on healthy eating, exercise, and healthy lifestyle improvements
- ^D I monitor patients' weight at the initiation of treatment with Seroquel® or Seroquel® XR
- ^a I monitor patients' weight on a regular basis after initiating treatment with Seroquel® or Seroquel® XR
- I monitor tests for hyperlipidemia in patients who are taking Seroquel or Seroquel® XR
- [□] I observe for signs and symptoms of hyperglycaemia in patients who are taking Seroquel® or Seroquel® XR
- I monitor patients with diabetes mellitus or with risk factors for diabetes mellitus for worsening of glucose control if they are taking Seroquel® or Seroquel® XR

Question 4

The following question has two parts; please respond to both parts of the question.

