3.2 Study Population

3.2.1 Inclusion Criteria

Health Care Professionals who were targeted to receive the metabolic educational materials and either currently prescribe or have the potential to prescribe SEROQUEL or SEROQUEL XR.

Each physician should meet all inclusion criteria and none of the exclusion criteria to be eligible for this survey. Under no circumstances can there be any exceptions to this rule.

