5. MEASURES TO MINIMIZE BIAS IN THE SAMPLE AND QUESTIONNAIRE ADMINISTRATION

Several measures will be used to minimize bias in the sample. Every effort will be made to ensure diversity in the distribution of healthcare providers invited to participate with regard to geography and physician specialty; however, the choice to ultimately participate in the survey is voluntary.

All participants who might have access to confidential information about this survey will be excluded. Also, Healthcare providers or their immediate family members employed by AstraZeneca or a European Regulatory Agency will not be eligible to participate.

An Internet survey will be convenient for respondents to participate since they can complete the questionnaire at any convenient time and location. Healthcare providers will be provided

with a unique code during the recruitment process and will then be asked to provide the unique code in order to gain access to the online survey. All respondents who are eligible to participate will answer the same questions outlined in Appendix B. The code will be inactivated after use to minimize fraud and reduce the chance of a respondent participating in the survey more than once. In order to minimize self-selection bias, a reminder notice will be sent to invited participants who have not responded within two weeks of the initial invitation.

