6. ANALYSIS

The survey questionnaire contains questions about the specialty of the physician sample completing the survey, questions specific to whether referrals are made to other healthcare providers for metabolic monitoring, whether the healthcare provider conducts monitoring of patients, general questions regarding receipt of the educational materials, and behavior about reading the materials. Information obtained from responses to each question of the survey will be reported as descriptive statistics. A frequency distribution of responses to each question (the number of respondents who give answers to each response option) will be presented.

Each risk minimization behavior will be evaluated individually.

Related behaviors, such as:

- Monitoring for weight
- Monitoring for signs and symptoms of hyperglycaemia and monitoring blood glucose changes in patients with diabetes mellitus will be combined to report the number of survey respondents who answered each risk minimization activity individually, any one activity and both activities. This will be expressed as a percent of the total number of respondents who answered the questions on these risk minimization activities.

Frequency distributions of the responses to having received SEROQUEL[®] / SEROQUEL[®] XR educational materials and behaviors about reading the educational materials, will also be calculated and displayed. The analysis of frequencies will include exact binomial 95% confidence intervals.

The following will be reported, as appropriate, as part of this analysis:

- The number of invitations issued to healthcare providers
- The number of healthcare providers screened for participation
- The number of healthcare providers eligible for participation
- The number of healthcare providers who completed the survey

- Description of healthcare provider survey participants, including:
 - Specialty of respondent
 - Country of practice
- Frequency distribution of responses to each survey question (the number of respondents who give each answer to each question)
- Percent of respondents selecting desired response to each question relating to each risk minimization activity and 95% confidence interval
- Percent of respondents demonstrating success of composite risk minimization activities and 95% confidence interval

Additional analyses may be performed as needed.

Risk Minimization Physician Survey Protocol

Drug Substance	Quetiapine fumarate
Study Code	D1443C000127
Edition Number	1

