Appendix B Questionnaire

QUESTIONNAIRE

The questionnaire is designed to be administered as an on-line survey via Internet. The following are mock-up version of what the successive screens that would be displayed

Screen 3 Question 1:

What is your medical specialty*? Please select one from the drop-down list below.

- O General Medicine/General Practice
- O Neurology
- O Psychiatry
- O Other SPECIFY:

* NOTE – OTHER SPECIALTIES TO BE INCLUDED BASED ON AUDIENCES TO WHOM MATERIAL WAS SENT

Screen 4 Question 2:

Instructions: Please think about your patients with schizophrenia, bipolar disorder, and/or major depressive disorder who are treated with Seroquel® or Seroquel® XR. Describe the "monitoring" of metabolic factors^{*} potentially related to treatment with Seroquel® or Seroquel® XR.

- What proportions of your patients are being monitored by you, someone else in A. your practice or are referred to other healthcare providers? %
- What proportion of your patients is referred to other healthcare providers for B. monitoring? %

*Monitoring of metabolic factors includes: weight at initiation and during continuing treatment, ordering or reviewing lipid panel tests, observing patients for signs or symptoms associated with hyperglycaemia, ordering or reviewing tests for blood glucose measurement for patients with diabetes mellitus or in patients with risk factors for diabetes mellitus for worsening of glycaemic control, and counseling on nutrition, exercise and maintaining a healthy lifestyle

Screen 5 Question 3:

Instructions: Thinking now of the patients that you yourself monitor for metabolic issues potentially related to treatment with Seroquel® or Seroquel® XR, which of the following activities do you perform? Please check all that apply.

GEL Version ID: CNS.000-362-594.2.0 Approved Date Printed: 04-Jan-2013 Approved by [name] 21 Dec 2012 15:02:47

- ^a I counsel patients taking Seroquel® or Seroquel® XR on healthy eating, exercise, and healthy lifestyle improvements
- I monitor patients' weight at the initiation of treatment with Seroquel® or Seroquel® XR
 I monitor patients' weight on a regular basis after initiating treatment with Seroquel® or
- Seroquel® XR
- [□] I monitor tests for hyperlipidemia in patients who are taking Seroquel or Seroquel® XR
- I observe for signs and symptoms of hyperglycaemia in patients who are taking Seroquel® or Seroquel® XR

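### Section 6 bases the Question 3 activity rates on those who answered, but a blank on that check-all list can mean none performed, skipped or not applicable

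*Protocol*

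**What the plan says.** - **Denominator.** For the individual, any-one and both-activity figures, Section 6 states: "This will be expressed as a percent of the total number of respondents who answered the questions on these risk minimization activities". The reporting list in the same section drops that restriction: "Percent of respondents selecting desired response to each question relating to each risk minimization activity and 95% confidence interval".
- **Question 3.** Section 3.1.1 asks "which of the following activities do you do? Please check all that apply" and Appendix B asks "which of the following activities do you perform? Please check all that apply". Both list the same six statements of things the provider does. Neither offers a box for none or for not applicable.
- **Stem.** Appendix B opens Question 3 with "Thinking now of the patients that you yourself monitor for metabolic issues". Section 3.1.1 also counts patients monitored by someone else in the practice.
- **Eligibility.** Section 3.2.1 admits providers who "either currently prescribe or have the potential to prescribe SEROQUEL or SEROQUEL XR".
- **Routing.** Section 5 states: "All respondents who are eligible to participate will answer the same questions outlined in Appendix B". No skip path is described for a provider without treated patients.
- **Contrast.** Section 3.1 says the receipt and reading questions "are closed-ended questions (answered affirmatively as yes/no/unsure response options", so Question 4 has an explicit negative answer and Question 3 does not.

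**The concern.** On a check-all list, a provider who performs none of the activities submits the same record as one who skipped the item: nothing ticked. If the percentage is then taken over those who answered, the natural reading removes that provider from the denominator, although this is exactly the provider who should count against the rate.

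The opposite error is also open. A potential prescriber with nobody on the product is eligible and sees the same questions. Questions 2 and 3 presuppose treated patients, so this provider can only enter 0% or leave blanks. Counted as a non-performer, the provider lowers the rate without having failed to monitor anyone. Providers who refer every patient also have nothing to tick in Question 3. Under the Appendix B stem, so do those whose colleagues do the monitoring.

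The activity and composite percentages are how the survey reports monitoring behaviour, and their confidence intervals reflect neither error. An analysis plan can define the denominator later, but it cannot recover an answer that respondents were never offered.

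**Working it through.** **The plan's own figure.** Section 3.3 gives 100 completed questionnaires per country, two-sided 95% intervals and a stated precision of 6 to 10 percentage points. Table 1 reproduces as p ± 1.96 × √(p(1 − p)/100), truncated at 0. At 51%: 1.96 × √(0.51 × 0.49/100) = 9.8 points, giving 41.2% to 60.8% as printed. At 81% it gives 73.3% to 88.7%, also as printed. All 17 rows agree to rounding. Table 1 is used here only as a yardstick for the shifts below.

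**Upward error: blanks from non-performers are dropped.** Let k be the number of 100 completers who tick an activity and b the number who perform none and leave Question 3 blank. The rate over all completers is k/100. The rate over those who answered is k/(100 − b), larger by the factor 100/(100 − b). The documents do not give b, so a range is assumed. Intervals are exact binomial, as Section 6 plans.

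| k | b | k/100 | k/(100 − b) | Shift (points) | Exact 95% CI after dropping |
|---|---|---|---|---|---|
| 60 | 5 | 60% | 63.2% | +3.2 | 52.6 to 72.8 |
| 60 | 10 | 60% | 66.7% | +6.7 | 55.9 to 76.3 |
| 60 | 20 | 60% | 75.0% | +15.0 | 64.1 to 84.0 |
| 80 | 5 | 80% | 84.2% | +4.2 | 75.3 to 90.9 |
| 80 | 10 | 80% | 88.9% | +8.9 | 80.5 to 94.5 |
| 80 | 20 | 80% | 100% | +20.0 | 95.5 to 100 |

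For k = 60 the shift passes 10 points when 60/(100 − b) > 0.70, that is from b = 15 (60/85 = 70.6%). For k = 80 it does so when 80/(100 − b) > 0.90, from b = 12 (80/88 = 90.9%).

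**Downward error: providers with no treated patients count as non-performers.** Let p be the true rate among treating providers and m the share of respondents with no treated patients. The reported rate is p(1 − m). The documents do not give m.

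- p = 80%: 0.80 × 0.95 = 76%; 0.80 × 0.90 = 72%; 0.80 × 0.80 = 64%.
- p = 60%: 57%, 54% and 48% at the same shares.

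**The two together.** One rule applied to all blanks cannot put both groups right. Dropping every blank rightly leaves out providers without patients but loses the non-performers. Counting every blank as not performed keeps the non-performers but wrongly charges the providers without patients.

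**The case against.** - **The denominator may not exclude anyone.** An unticked box on a submitted questionnaire can be read as not performed, and the reporting list speaks of respondents without restriction. This stands in part. A reader might infer that the plan is shown to inflate the rates; the documents do not support that, because they never say how a blank is treated. The two wordings in Section 6 do, however, leave the denominator unsettled, and reading every blank as not performed brings in the downward error.
- **Question 2 helps to interpret a blank.** A provider who monitors nobody can enter 0% in part A, and one who refers everyone can enter equal values in A and B. Section 3.1 also describes the outcome measures as physician-supplied percentages, which is the Question 2 format. This is partial mitigation. A 0% does not separate no patients from none monitored, and nothing links Question 2 to the Question 3 denominator.
- **Few invitees may lack patients.** Section 3.4 draws the sample from those thought likely to prescribe. That should shrink the group, but Section 3.2.1 still admits potential prescribers, and screening on the stated criteria would not remove them.
- **Readers can recompute.** Section 6 reports the number of completers and the response counts, so a rate over all completers can be rebuilt. That rate still cannot tell a non-performer from a provider with nobody to monitor.
- **The composites.** A reader might also infer that the any-one-activity figure must lie near 100%. Section 6 does not support this: it combines related behaviours (weight; hyperglycaemia signs with glucose monitoring), not the whole list, so someone who ticks only counselling or lipids does not count.
- **The survey is descriptive.** Section 3.3 sets no success threshold, so no pass/fail decision turns on the bias. That is true, but the estimates are the product of the survey.

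**Conclusion.** The point holds as a defect of the question format and the denominator. A blank Question 3 has three possible meanings, the protocol assigns none of them, and it uses two different wordings for the denominator. Depending on the rule adopted, the activity and composite rates are pushed up by the factor 100/(100 − b) or down by the factor (1 − m).

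With 5 blanks per 100, or 5% without treated patients, the shift is about 3 to 4 points at the rates shown, inside the stated precision. At 10 it is about 6 to 9 points, comparable with it. At 20 it is 12 to 20 points, beyond it. Both b and m are assumptions, and the documents fix neither the size nor the net direction. The conclusion rests on the response options as printed in Section 3.1.1 and Appendix B and on the eligibility rule in Section 3.2.1.

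**What to change.** Before translation and fielding:

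1. **Question 2:** add an exclusive answer, *I currently treat no patients with SEROQUEL or SEROQUEL XR*, that skips to Question 4.
2. **Question 3:** add two separate exclusive boxes, *None of these* and *I refer all patients to other providers for monitoring*. A single combined box could not be reported as two categories.
3. **Stem:** use one Question 3 stem in Section 3.1.1 and Appendix B, and decide whether monitoring by practice colleagues counts.
4. **Section 6:** replace the denominator sentence with *all completers who currently treat at least one patient with the product*, and use it in the reporting list too. Count *None of these* as not performed. Report refer-all and any remaining blanks as separate categories.
5. **Question 4:** keep providers with no treated patients in the receipt and reading analyses.

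The cost is three response options, one harmonised stem and a revised denominator. The Question 2 and Question 3 denominators may fall somewhat below 100 in some countries, with slightly wider intervals there.

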Appendix B Questionnaire

QUESTIONNAIRE

The questionnaire is designed to be administered as an on-line survey via Internet. The following are mock-up version of what the successive screens that would be displayed

Screen 3 Question 1:

What is your medical specialty*? Please select one from the drop-down list below.

- O General Medicine/General Practice
- O Neurology
- O Psychiatry
- O Other SPECIFY:

* NOTE – OTHER SPECIALTIES TO BE INCLUDED BASED ON AUDIENCES TO WHOM MATERIAL WAS SENT

Screen 4 Question 2:

Instructions: Please think about your patients with schizophrenia, bipolar disorder, and/or major depressive disorder who are treated with Seroquel® or Seroquel® XR. Describe the "monitoring" of metabolic factors^{*} potentially related to treatment with Seroquel® or Seroquel® XR.

- What proportions of your patients are being monitored by you, someone else in A. your practice or are referred to other healthcare providers? %
- What proportion of your patients is referred to other healthcare providers for B. monitoring? %

*Monitoring of metabolic factors includes: weight at initiation and during continuing treatment, ordering or reviewing lipid panel tests, observing patients for signs or symptoms associated with hyperglycaemia, ordering or reviewing tests for blood glucose measurement for patients with diabetes mellitus or in patients with risk factors for diabetes mellitus for worsening of glycaemic control, and counseling on nutrition, exercise and maintaining a healthy lifestyle

Screen 5 Question 3:

Instructions: Thinking now of the patients that you yourself monitor for metabolic issues potentially related to treatment with Seroquel® or Seroquel® XR, which of the following activities do you perform? Please check all that apply.

GEL Version ID: CNS.000-362-594.2.0 Approved Date Printed: 04-Jan-2013 Approved by [name] 21 Dec 2012 15:02:47

- ^a I counsel patients taking Seroquel® or Seroquel® XR on healthy eating, exercise, and healthy lifestyle improvements
- I monitor patients' weight at the initiation of treatment with Seroquel® or Seroquel® XR
 I monitor patients' weight on a regular basis after initiating treatment with Seroquel® or
- Seroquel® XR
- [□] I monitor tests for hyperlipidemia in patients who are taking Seroquel or Seroquel® XR
- I observe for signs and symptoms of hyperglycaemia in patients who are taking Seroquel® or Seroquel® XR

I monitor patients with diabetes mellitus or with risk factors for diabetes mellitus for worsening of glucose control if they are taking Seroquel® or Seroquel® XR

Screen 6 Question 4:

Instructions: The following question has two parts; please respond to both parts of the question

- A. Did you receive educational information relevant to the issues in this survey from AstraZeneca, either as a mailing or from a company representative, in (INSERT LOCAL MARKET REFERENCE MONTH) 2012 regarding the Product Label for Seroquel® or Seroquel® XR?
 - O Yes
 - O No
 - O Do not know/not sure

B. Did you read the educational information?

- O Yes
- O No
- O Do not know/not sure

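### Question 3 asks respondents to tick the six activities that the preceding screen has just defined as monitoring, so its rates are likely to be biased upward by an unknown amount

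*Protocol*

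**What the plan says.** Appendix B presents the questionnaire as a "mock-up version of what the successive screens that would be displayed", so the order of the screens is part of the design. Section 3.1.1 gives Questions 2 and 3 in the same order.

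- **Screen 4 (Question 2)** asks for two percentages: patients monitored by any route, and patients referred elsewhere. Its footnote defines the term, beginning "Monitoring of metabolic factors includes: weight at initiation and during continuing treatment, ordering or reviewing lipid panel tests" and ending "and counseling on nutrition, exercise and maintaining a healthy lifestyle".
- **Screen 5 (Question 3)** follows directly and asks "which of the following activities do you perform? Please check all that apply". One of its options is "I counsel patients taking Seroquel® or Seroquel® XR on healthy eating, exercise, and healthy lifestyle improvements"; another, further down the list, is "I monitor tests for hyperlipidemia in patients who are taking Seroquel or Seroquel® XR". All six are affirmative statements. There is no 'none of these', no yes/no per item and no frequency scale.
- **Section 6** reports the percentage giving the response counted as desired for each activity. It also reports composites (each activity, any one, both) for weight and for hyperglycaemia/glucose, all with 95% confidence intervals. Only Question 3 collects these activities item by item.
- **Section 5** opens with "Several measures will be used to minimize bias in the sample". It then lists diversity of invitees, exclusions, convenience of the internet format, single-use codes and a reminder.
- **Section 4.1.1** has two providers look for items that are hard to understand or open to misreading.
- **Section 3.3** reads the confidence interval as showing that the true population level is no lower than its lower limit.

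**The concern.** By Screen 5, a respondent has read what monitoring consists of and has stated the percentage of patients monitored on that definition. Leaving one of the same activities unticked then sits awkwardly with the figure just given. A respondent who does not perform an activity can respond to this pressure only by adding a tick, so the expected direction is upward.

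The Question 3 rates and their composites are outcome measures of the survey. It has no comparison group and no measurement before the materials went out, so a shift in level would not cancel. Later analysis cannot recover unprompted answers that were never collected. The lower-limit reading in Section 3.3 is also unsafe if self-report is inflated.

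**Working it through.** **Step 1. Compare the two screens (Appendix B).**

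| Screen 4 definition | Screen 5 option | Match |
|---|---|---|
| Weight at start | Weight at start | Same |
| Weight during treatment | Weight regularly after start | Close; Screen 5 adds regularity |
| Lipid panel tests | Tests for hyperlipidaemia | Same in substance |
| Signs or symptoms of hyperglycaemia | Signs and symptoms of hyperglycaemia | Same |
| Glucose tests in diabetic or at-risk patients | Worsening glucose control in those patients | Close; Screen 5 names no test |
| Lifestyle counselling | Lifestyle counselling | Same |

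All six elements correspond, with small differences in wording. Screen 5 has no further option.

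**Step 2. Look for a safeguard.** The measures in Section 5 concern who takes part and how often. The check in Section 4.1.1 concerns comprehension. Neither deals with prompting or over-reporting.

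**Step 3. Reproduce the stated precision.** Table 1 (Section 3.3) uses n = 100 and two-sided 95% limits. The formula p ± 1.96·√(p(1-p)/100), cut at zero, reproduces all 17 rows. At 51%, 1.96·√(0.51·0.49/100) = 0.098, giving 41.2% to 60.8%. The largest half-width is 9.8 points. The exact interval planned in Section 6 is 40.8% to 61.1% at 51%, so the choice of interval matters little here.

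**Step 4. Size the bias under an assumption.** Let p be the true share performing an activity and f the share of non-performers who tick it anyway. The protocol gives no value for f; 10% to 30% is assumed.

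Reported rate = p + (1-p)f, so bias = (1-p)f.

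| True p | f | Reported | Bias (points) | Exact 95% CI covers p, n = 100 |
|---|---|---|---|---|
| 50% | 10% | 55% | +5 | 86% |
| 50% | 20% | 60% | +10 | 54% |
| 50% | 30% | 65% | +15 | 17% |
| 70% | 10% | 73% | +3 | 93% |
| 70% | 20% | 76% | +6 | 79% |
| 70% | 30% | 79% | +9 | 54% |

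At p = 50%, the bias equals the 9.8-point half-width when f = 9.8/50 = 19.6%. At p = 90% and f = 20%, it is only 0.10·0.20 = 2 points. For a composite, read p as the true share meeting it and f as the share of the rest who tick enough to be counted. The size therefore differs by item and composite.

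**Step 5. Effect of sample size.** The bias does not depend on n. If the eight countries were pooled (8 × 100 = 800), p = 50% and f = 10% would still give +5 points, and coverage would fall to about 21%.

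**The case against.** A reader might infer that Screen 4 is an answer key, that every box is a correct answer, and that all six rates are therefore inflated by some 10 points. The documents do not support this, for four reasons.

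- Question 3 asks about behaviour, not knowledge. A physician who does all six things should tick all six.
- The protocol never defines the desired response option by option. The key messages in Section 2 do not name counselling, and they speak of managing lipid changes rather than testing for them.
- A 10-point figure needs f = 20% at p = 50%. Both values are assumptions, and the bias shrinks as p rises.
- The fee is for time on completion, whatever is ticked, so it is no evidence of bias in one direction.

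Other points also limit the concern. Screen 5 displays the six activities itself, so a respondent inclined to over-tick would see them without the footnote, and the separate contribution of Screen 4 cannot be isolated. The survey is self-completed online, identities are stored apart from answers, and the consent calls the study non-promotional. The question on receipt of materials comes last, so it does not prime Question 3. A companion medical-records evaluation is proposed, and Section 3.3 sets no success threshold, so no prespecified decision would flip.

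All of this stands as a limit on strength. It does not remove the consistency pressure from answering Question 2 under the definition first, and it supplies no measure against over-reporting. Deferring the matter to the analysis plan would not help, because the weakness lies in how the answers are collected.

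**Conclusion.** The point holds as a design weakness that is cheap to reduce before fielding. The Question 3 activity rates, and the weight and glucose composites, are likely to be biased upward. The document does not show that they are, and it gives no basis for a size. Under the assumed f of 10% to 30%, the bias runs from +5 to +15 points at a true rate of 50% and from +3 to +9 at 70%. That ranges from well inside to beyond the largest sampling half-width of 9.8 points.

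This rests on the assumption that over-reporting outweighs omitted ticks, which fits the direction of the prompt but is untested. It does not extend to the Question 2 percentages, where the footnote serves as a needed definition and its effect is less clear. No sample-size figure changes.

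**What to change.** In Appendix B and Section 3.1.1:

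- Ask the activity question (now Question 3) before the screen carrying the Question 2 definition, and block back-navigation. Adjust the stem, which now follows on from Question 2.
- Keep the definition on the Question 2 screen. Its percentages have no clear meaning without it. Respondents would then see the activity list before Question 2, but that screen shows the list anyway.
- Randomise the order of the activity options and add 'none of these'. Without that option, an empty screen could mean no activity or no answer, and Section 6 counts only those who answered.

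In Section 3.3, state that the confidence interval covers sampling error only, so its lower limit is not a floor for true monitoring if self-report is inflated.

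Do not exclude respondents who tick every option, since that would drop the most thorough monitors. Foil items are optional. In a behaviour question they could only indicate over-ticking, because some physicians may truly perform the extra activity.

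The cost is minor rewording, translation of one more option, some reprogramming, and possibly less favourable reported rates. Social desirability from the activity list itself would remain.
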